15.0 Statistical Considerations

This is a Phase II open-label study designed to determine the safety and efficacy of nivolumab and lirilumab, as single agents or in combination and with 5-azacitidine, in patients with myelodysplastic syndromes (MDS). Two different patient groups (lower risk MDS and High MDS) with 2 cohorts each will be study. Each cohort will be composed of N=20 patients. Accrual will be parallel for each patient group.

The primary efficacy outcome for each cohort is the overall response rate (ORR) defined as CR + PR + hematological improvement (HI). Overall response will be assessed after 6 cycles of treatment; cycle length is 28 days. A maximum of 20 total evaluable patients will be enrolled in each cohort (N=80).

Lower Risk MDS cohorts: cohorts (1 and 2): each cohort separately

The target ORR with the experimental treatment (i.e. lirilumab alone or in combination with nivolumab) is 70%, assuming the standard treatment ORR is 50%. The regimen of the experimental treatment will be considered worthy of further investigation if it elicits an increase in ORR to 70% with acceptable toxicity. A >30% therapy related non-hematological grade 3/4 toxicity rate is considered unacceptable. Thus, interim

monitoring rules, assuming the prior distributions above, were constructed that meet the following two conditions,

- 1) Stop if $\text{Prob}\{p(\text{ORR}, E) < p(\text{ORR}, H) + 0.20 \mid \text{data}\} > 0.95$, or
- 2) Stop if $\text{Prob}\{p(\text{TOX}, E) > 0.30 \mid \text{data}\} > 0.975$,
- 3) where $P(\text{ORR}, E)$ and $P(\text{TOX}, E)$ are the true ORR and toxicity rates for the combination treatment, and $p(\text{ORR}, H)$ is the true ORR rate of the standard treatment. The first rule provides for stopping the study if the data suggest that it is unlikely (i.e., probability < 5.0%) that ORR rate of the experimental treatment is greater than the ORR rate of standard treatment by 20.0%. The second condition will stop the study early if excessive therapy-related non-hematological grade 3/4 toxicity (>30.0%) is highly probable (i.e., probability >97.5%) for the experimental treatment. Monitoring for toxicity and futility will start when the first patient has been evaluated, and cohort size for future evaluations is 5.

The monitoring rule for the toxicity rate, based on these assumptions and monitoring conditions above is found in Table 1. For example, accrual will cease if 4 or more patients experience toxicities among the first 5 patients.

Table 1. Stop accrual if the number of drug-related non-hematological grade 3/4 toxicities is greater than or equal to indicated (i.e., # patients with toxicities) among the number of patients evaluated				
# patients evaluated	5	10	15	20
# patients with toxicities	4-5	7-10	9-15	Always stop with this many patients

Monitoring the ORR rate, based on the above assumptions and monitoring conditions is found in Table 2. For example, accrual will cease if 1 patient experience an overall response within 6 cycles in the first 5 patients treated.

Table 2. Stop accrual if the number with overall response is less than or equal to indicated (i.e., # patients with overall response) among the number of patients evaluated				
# patients evaluated	5	10	15	20
# patients with overall response	1	4	7	Always stop with this many patients

Multc Lean Desktop (version 2.1.0) was used to generate the toxicity and futility stopping boundaries and the OC table (Table 3). In order to utilize the software for the design, a response constant rate of 50% and beta (1.0, 1.0) priors were assumed for

the standard treatment response distribution and experimental treatment response prior distribution, respectively. A delta 20% was assumed. In addition, a 30% toxicity constant rate and beta (0.6, 1.4) priors were assumed for the standard treatment toxicity constant rate and experimental treatment toxicity prior distribution, respectively.

The probability of stopping the study early if the true ORR of the experimental treatment was 70% and the true toxicity rate was 30% was 12.4%. Probabilities of stopping early for high true toxicity rates (i.e., 50%) were 72.6% when the true ORR was 50%, and 43.2% when true ORR rate was 70%.

Table 3. Operating characteristics for simultaneous monitoring response and toxicity rates for patients treated with experimental treatment		
True Toxicity Rate	True ORR	Prob(stop the trial early)
0.10	0.50	0.5590
	0.60	0.2739
	0.70	0.0849
	0.80	0.0137
	0.90	0.0010
0.20	0.50	0.5621
	0.60	0.2790
	0.70	0.0914
	0.80	0.0207
	0.90	0.0081
0.30	0.50	0.5779
	0.60	0.3050
	0.70	0.1241
	0.80	0.0560
	0.90	0.0439
0.40	0.50	0.6271
	0.60	0.3861
	0.70	0.2263
	0.80	0.1661
	0.90	0.1554
0.50	0.50	0.7261
	0.60	0.5490
	0.70	0.4316
	0.80	0.3874
	0.90	0.3795

High Risk MDS cohorts (3 and 4): each cohort separately

The target ORR with the experimental treatment (i.e. 5-azacitidine in combination with lirilumab, or combination of 5-azacitidine, Lirilumab and nivolumab) is 70%, assuming the standard treatment ORR is 50%. The regimen of the experimental treatment will be considered worthy of further investigation if it elicits an increase in ORR to 70% with acceptable toxicity. A >30% therapy related non-hematological grade 3/4 toxicity rate is considered unacceptable. Thus, interim monitoring rules, assuming the prior distributions above, were constructed that meet the following two conditions,

- 1) Stop if $\text{Prob}\{p(\text{ORR}, E) < p(\text{ORR}, H) + 0.20 \mid \text{data}\} > 0.95$, or
- 2) Stop if $\text{Prob}\{p(\text{TOX}, E) > 0.30 \mid \text{data}\} > 0.975$,
- 3) where $P(\text{ORR}, E)$ and $P(\text{TOX}, E)$ are the true ORR and toxicity rates for the combination treatment, and $p(\text{ORR}, H)$ is the true ORR rate of the standard treatment. The first rule provides for stopping the study if the data suggest that it is unlikely (i.e., probability < 5.0%) that ORR rate of the experimental treatment is greater than the ORR rate of standard treatment by 20.0%. The second condition will stop the study early if excessive therapy-related non-hematological grade 3/4 toxicity (>30.0%) is highly probable (i.e., probability >97.5%) for the experimental treatment. Monitoring for toxicity and futility will start when the first patient has been evaluated, and cohort size for future evaluations is 5.

The monitoring rule for the toxicity rate, based on these assumptions and monitoring conditions above is found in Table 4. For example, accrual will cease if 4 or more patients experience toxicities among the first 5 patients.

Table 4. Stop accrual if the number of drug-related non-hematological grade 3/4 toxicities is greater than or equal to indicated (i.e., # patients with toxicities) among the number of patients evaluated				
# patients evaluated	5	10	15	20
# patients with toxicities	4-5	7-10	9-15	Always stop with this many patients

Monitoring the ORR rate, based on the above assumptions and monitoring conditions is found in Table 5. For example, accrual will cease if 0 patients experience an overall response within 6 cycles in the first 5 patients treated.

Table 5. Stop accrual if the number with overall response is less than or equal to indicated (i.e., # patients with overall response) among the number of patients evaluated				
# patients evaluated	5	10	15	20
# patients with overall response	1	4	7	Always stop with this many patients

Multc Lean Desktop (version 2.1.0) was used to generate the toxicity and futility stopping boundaries and the OC table (Table 6). In order to utilize the software for the design, a response constant rate of 50% and beta (1.0, 1.0) priors were assumed for the standard treatment response distribution and experimental treatment response prior distribution, respectively. A delta 20% was assumed. In addition, a 30% toxicity constant rate and beta (0.6, 1.4) priors were assumed for the standard treatment toxicity constant rate and experimental treatment toxicity prior distribution, respectively.

The probability of stopping the study early if the true ORR of the experimental treatment was 70% and the true toxicity rate was 30% was 12.4%. Probabilities of stopping early for high true toxicity rates (i.e., 50%) were 72.6% when the true ORR was 50%, and 43.2% when true ORR rate was 70%.

Table 6. Operating characteristics for simultaneous monitoring response and toxicity rates for patients treated with experimental treatment		
True Toxicity Rate	True ORR	Prob(stop the trial early)
0.10	0.50	0.5590
	0.60	0.2739
	0.70	0.0849
	0.80	0.0137
	0.90	0.0010
0.20	0.50	0.5621
	0.60	0.2790
	0.70	0.0914
	0.80	0.0207
	0.90	0.0081
0.30	0.50	0.5779
	0.60	0.3050

	0.70	0.1241
	0.80	0.0560
	0.90	0.0439
0.40	0.50	0.6271
	0.60	0.3861
	0.70	0.2263
	0.80	0.1661
	0.90	0.1554
0.50	0.50	0.7261
	0.60	0.5490
	0.70	0.4316
	0.80	0.3874
	0.90	0.3795

Statistical Analysis Plan

All patients who received any dose of the study agent will be included in the analysis for efficacy and safety. Demographic/clinical characteristics (i.e. including duration of response) and safety data of the patients will be summarized using descriptive statistics such as mean, standard deviation, median and range. For the primary efficacy analysis, we will estimate the ORR for the experimental treatments, along with the 95% credible intervals. The association between ORR and patient's clinical characteristics will be examined by Wilcoxon's rank sum test or Fisher's exact test, as appropriate. Toxicity type, severity and attribution will be summarized for each patient using frequency tables. The distribution of time-to-event endpoints (PFS and OS) including overall survival and event free survival will be estimated using the method of Kaplan and Meier. Comparisons of time-to-event endpoints by important subgroups will be made using the log-rank tests. Paired t-tests will be used to determine the immunological and molecular changes in the peripheral blood and bone marrow from baseline to the time of response, and to the time of disease progression.

16. Confidentiality Plan

Confidentiality will be maintained via codification of data collected and restriction of access to the data. In particular, to be authorized to use the PDMS database, M. D.

Anderson employees must have an institutional USERID assigned through the Information Services Security Department. State regulations for database computer access are followed. ALL database analysts regularly log and monitor the system access and log-in activity. All unsuccessful attempts to access the ALL database are logged to a file that is reviewed daily by the ALL database coordinator. If the user has updated patient data, they will be prompted for the password upon exiting the ALL database. If the password is not verified, an automated e-mail is sent to the ALL database coordinator, and a log is created. Users are required to change their password every three months. The passwords are stored in an encrypted format.

Unless specifically described and explained to the clinical trial participants in the informed consent document, results of the study will not be shared with the patients. The profiles will be obtained on coded samples with no patient identifiers, and confidentiality will be maintained. Results of the clinical trial will be entered in clinicaltrials.gov, but individual patient's results will remain confidential information.

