10.0 Evaluation during Treatment

All evaluations can vary +/- 3 days.

Complete history and physical and assessments for toxicity should be performed weekly for the first course, then once per course.

CBC, platelet count, differential, creatinine, albumin, SGPT, electrolytes, total bilirubin, and TSH weekly for the first course, then once per course at the discretion of the treating physician.

Bone marrow aspiration with cytogenetics (if abnormal at baseline) on Day 28 of Course 1 (+/- 3 days) and afterwards every 3 months or as indicated to document response or to decide on therapy administration. Once a response is obtained, bone marrow sampling can be repeated at the discretion of the treating physician to confirm remission status or document loss of response.

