12.0 Reporting of Adverse Events

Baseline events will be recorded in the medical history section of the case report form and will include the terminology event name, grade, and start date of the event.

Baseline events are any medical condition, symptom, or lab abnormality present before the informed consent is signed. If exact start date is unknown, month and year or year may be used as the start date of the baseline event.

The maximum grade of the adverse event will be captured per cycle.

Serious Adverse Event Reporting (SAE) Language for M. D. Anderson-sponsored IND Protocols

An adverse event or suspected adverse reaction is considered “serious” if, in the view of either the investigator or the sponsor, it results in any of the following outcomes:

- Death
- A life-threatening adverse drug experience – any adverse experience that places the patient, in the view of the initial reporter, at immediate risk of death from the adverse experience as it occurred. It does not include an adverse experience that, had it occurred in a more severe form, might have caused death.
- Inpatient hospitalization or prolongation of existing hospitalization
- A persistent or significant incapacity or substantial disruption of the ability to conduct normal life functions.
- A congenital anomaly/birth defect.

Important medical events that may not result in death, be life-threatening, or require hospitalization may be considered a serious adverse drug experience when, based upon appropriate medical judgment, they may jeopardize the patient or subject and may require medical or surgical intervention to prevent one of the outcomes listed in this definition. Examples of such medical events include allergic bronchospasm requiring intensive treatment in an emergency room or at home, blood dyscrasias or convulsions that do not result in inpatient hospitalization, or the development of drug dependency or drug abuse (21 CFR 312.32).

- **Important medical events as defined above, may also be considered serious adverse events. Any important medical event can and should be reported as an SAE if deemed appropriate by the Principal Investigator or the IND Sponsor, IND Office.**

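### Does the toxicity stopping rule fail because no period is given over which toxicity is evaluated?

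*Combined protocol and SAP*

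**What the plan says.** Section 15.0 gives each cohort of 20 two interim rules, one for futility and one for toxicity, and starts them together: "Monitoring for toxicity and futility will start when the first patient has been evaluated, and cohort size for future evaluations is 5". The same wording serves the lower-risk and the higher-risk cohorts.

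For response the time point is explicit: "Overall response will be assessed after 6 cycles of treatment; cycle length is 28 days". The futility example above Table 2 repeats it: "For example, accrual will cease if 1 patient experience an overall response within 6 cycles in the first 5 patients treated".

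For toxicity the limit is "A >30% therapy related non-hematological grade 3/4 toxicity rate is considered unacceptable", and the example above Table 1 is "For example, accrual will cease if 4 or more patients experience toxicities among the first 5 patients". Neither gives a period. The tables count patients *evaluated*, a word that is not defined for toxicity. Nothing is said about patients still under observation at a look, or about whether accrual pauses.

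Other sections show what safety data arrive and when. Section 10.0: "Complete history and physical and assessments for toxicity should be performed weekly for the first course, then once per course". Section 12.0: "The maximum grade of the adverse event will be captured per cycle". Neither is tied to the stopping rule. Section 7.0 lets a cohort be closed on accumating experience and sets delay and discontinuation criteria for individual patients.

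**The concern.** Safety is the primary objective (section 1.0), and this is the only numerical safety rule at cohort level. Its one action is to stop accrual, so its value depends on when it acts. Three readings can be put on *evaluated*:

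- **A.** Six cycles for both rules. The first toxicity look then falls 168 days after patient 5 starts, when much of the cohort may already be enrolled.
- **B.** The first course, the only period with weekly toxicity assessment. Later events would then be missed.
- **C.** Events count as they occur among the first 5, 10 and 15 patients.

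If the readings gave very different protection and the text could not separate them, the stopping probabilities quoted in section 15.0 could not be attached to one rule.

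**Working it through.** **Inputs from section 15.0.** Toxicity prior Beta(0.6, 1.4), limit 0.30, cutoff 0.975. Response prior Beta(1, 1), limit 0.50 + 0.20 = 0.70, cutoff 0.95. Looks at 5, 10 and 15; maximum 20.

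**Reproducing the plan.** With x toxicities in n patients, stop if Pr(p > 0.30) > 0.975 under Beta(0.6 + x, 1.4 + n − x).

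| n | posterior one below the bound | posterior at the bound |
|---|---|---|
| 5 | x = 3: 0.8745 | x = 4: 0.9751 |
| 10 | x = 6: 0.9625 | x = 7: 0.9914 |
| 15 | x = 8: 0.9597 | x = 9: 0.9878 |

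The bounds are 4, 7 and 9, as tabled. The futility bounds come out as 1, 4 and 7, also as tabled. At n = 1 the largest posteriors are 0.789 (toxicity) and 0.910 (futility). No stop is possible there, so the first usable look is at 5.

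Exact binomial recursion over the three looks gives these probabilities that the toxicity rule alone stops:

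- 50% toxicity: 0.1875 + 0.0684 + 0.1233 = 0.3792
- 30% toxicity: 0.0308 + 0.0048 + 0.0077 = 0.0433

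Futility alone stops 0.5588 at ORR 50% and 0.0844 at ORR 70%. Joint stopping is 1 − (1 − T)(1 − F):

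- 50% toxicity, ORR 50%: 1 − 0.6208 × 0.4412 = 0.7261
- 50% toxicity, ORR 70%: 1 − 0.6208 × 0.9156 = 0.4316

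Both match Table 3. All 25 entries match to within 0.00005, and Table 6 is identical. These figures take toxicity as one probability that is fully known at each look. They therefore hold for any window, provided the true rate is the rate in that window.

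**Assumptions for timing.** The documents give no accrual rate and no toxicity timing. Accrual is taken as evenly spaced at 0.5, 1, 2 or 3 patients per month per cohort. Six cycles are 168 / 30.44 = 5.52 months. True six-cycle toxicity is 50%.

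**Reading A, accrual not paused.** Enrolled at look k = min(20, k + floor(rate × 5.52)). A look acts only if fewer than 20 are enrolled.

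| rate per month | enrolled at looks 5/10/15 | stop while accrual is open |
|---|---|---|
| 0.5 | 7/12/17 | 0.3792 |
| 1 | 10/15/20 | 0.1875 + 0.0684 = 0.2559 |
| 2 | 16/20/20 | 0.1875 |
| 3 | 20/20/20 | 0 |

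If accrual pauses at each look, enrolment is 5/10/15 and the full 0.3792 acts at every rate.

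**Reading C.** Simulation with events confined to six cycles, under constant risk or with half of the events in course 1:

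| rate per month | stop with fewer than 20 enrolled | mean enrolled at the stop |
|---|---|---|
| 0.5 | 0.379 | 9.4–9.5 |
| 1 | 0.374–0.376 | 10.6–11.1 |
| 2 | 0.300–0.317 | 13.6–14.4 |
| 3 | 0.217–0.243 | 16.1–17.1 |

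The chance of ever reaching a bound stays 0.379, and at 30% toxicity it stays 0.043.

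**Reading B.** Under constant risk the course-1 rate is 1 − 0.5^(1/6) = 0.109, and the toxicity rule stops 0.07%. If 50% or 75% of the events fall in course 1 (rates 0.25 and 0.375), it stops 2.0% or 11.7%. These are toxicity-only figures and must not be set beside the joint 72.6% and 43.2%. The like-for-like joint figures under constant risk are 1 − 0.9993 × 0.4412 = 55.9% and 1 − 0.9993 × 0.9156 = 8.5%. In addition, if the window were course 1, the 50% in Table 3 would be a course-1 rate and the table would again be right.

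**Which reading the text favours.** The two worked examples differ. The futility example carries the six-cycle qualifier. The toxicity example has no qualifier and stops once four of the first five have had an event. That reads as a running count, and such a count is workable because toxicity is assessed throughout and graded per cycle. Nothing links the rule to course 1; weekly visits there are a schedule.

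**The case for a change.** The strongest case for a change is that the tables count patients *evaluated*, and the starting sentence is shared with an endpoint that takes 168 days. A literal reader could wait. At 2 or 3 patients per month without a pause, a literal wait cuts the chance of stopping in time to 18.8% or 0%, against 30–32% or 22–24% when events are counted as they occur. Clarifying the wording would take little text.

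Part of this stands. The period is missing, and so is any statement on pending patients or on accrual at a look. Even on the natural reading, the probability of stopping before the cohort is full depends on accrual, which Tables 3 and 6 do not show. A running count also needs a cut-off, because treatment may continue past cycle 6. With constant risk, a 30% six-cycle rate becomes 1 − 0.7² = 51% over 12 cycles. If every patient were followed that long and all events counted, a bound would be reached in about 41% of cohorts instead of 4.3%.

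The rest does not carry. The low figures under Reading A need both an assumed accrual rate and no pause. Those under Reading B need a window that no section supports, with late or evenly spread events. A stated window could not be derived from the documents either: a long one includes late events, and a short one misses them and needs its own justification for 30%. That choice belongs to the sponsor.

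**Conclusion.** No change to the plan follows. This is missing operational detail in a rule whose numbers are right: bounds 4/7/9, toxicity-only stopping of 37.9% at 50% and 4.3% at 30%, and every entry of Tables 3 and 6. The team running the cohorts would sensibly count qualifying events as they are graded, which the worked example already suggests and the planned data allow. With a six-cycle window, the chance of stopping a 50%-toxic cohort before 20 are enrolled is then about 38% at 0.5 patients per month, 37–38% at 1, 30–32% at 2 and 22–24% at 3. These figures rest on assumed accrual and event timing. The claim that the rule would almost never act is not supported.

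The rule is also not the only protection. Section 7.0 allows a cohort to be closed at discretion and sets individual discontinuation criteria, and section 12.0 requires serious events to reach the supporting company within 24 hours, although not every grade 3/4 event is serious. Whoever reports the stopping probabilities should say which window was used and that the tables assume complete toxicity data at each look.

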2.0 Background and hypothesis

MDS consists of an heterogeneous group of myeloid malignancies characterized by bone marrow failure and increased risk of transformation to acute myelogenous leukemia (AML) ¹. In general, patients are classified using IPSS criteria², and more recently IPSS-R³, into a lower risk (low, int-1) and higher risk (int-2, high risk) category. The standard of care for most patients with MDS, except for those with an alteration of chromosome 5, is a hypomethylating agent such as 5-azacitidine¹. Although this class of agents has significant activity in MDS and has been shown to improve survival ¹, duration of response is usually limited and the prognosis of patients with HMA failure is extremely poor⁴. Therefore, the need for new therapies and combinations for this group of patients.

Several groups have reported on the expression of Kir ligands and receptors in myeloid leukemias⁵. Our group has also reported up regulation of innate immunity signals and the PD1/PDL1 axis in MDS and the fact that expression is up regulated by treatment with a hypomethylating agent^{6,7}. We therefore hypothesized that immune checkpoints maybe involved in resistance to HMA agents and therefore maybe clinically synergistic with HMAs ref. To test these concepts, we propose a study where different cohorts of patients with MDS are treated either with single agent immune checkpoint inhibitor (nivolumab) in combination with an antibody against KIR (lirilumab) and with 5-azacitidine. Data from this pilot trial will allow us to determine the toxicity profile of these agents in MDS and the potential for clinical activity that could then guide larger definitive clinical trials for more specific subsets of patients.

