7.0 Treatment Plan

We plan to study 2 different patient groups (lower risk MDS [defined as low and int-1 by IPSS] and higher risk [defined as int-2 and high risk by IPSS]) with 2 cohorts each. Each cohort will be composed of N=20 patients. Accrual to cohort will be sequential in each patient group. Accrual will be parallel for each patient group.

All treatments can vary +/- 3 days.

1. Lower Risk MDS cohorts (Low and Int-1):

- Cohort 1: Lirilumab single agent Q4 wks.
- Cohort 2: Lirilumab Q4 weeks+ Nivolumab, Q2 wks X 9 cycles then both Q4 wks.

2. Higher Risk MDS cohorts (Int-2 and High):

- Cohort 3: 5-azacitidine IV, D1-7 of 28 day cycle, in combination with Lirilumab IV on D7

- Cohort 4: 5-azacitidine IV, D1-7 of 28 day cycle, in combination with Lirilumab IV Day 7 and Nivolumab IV D7 & D21 X 9 cycles then D7 only on Cycle 10 +

Specific cohorts can be closed based on ongoing experience with this trial or other relevant information.

Patients will receive study drug(s) according to the following treatment plan. Individual minor variations in the initiation of therapy, are acceptable as indicated by patient condition and physician judgment. These variations should be documented in the patient's medical record.

Dosing calculations for Nivolumab and 5-Azacitidine will be based actual body weight.

Single agent:

Lirilumab: Patient will receive lirilumab 3 mg/kg IV over approximately 60 minutes every 4 weeks. One cycle is defined as 4 weeks.

Combination:

Lirilumab and Nivolumab: Patient will receive Nivolumab 3 mg/kg IV over approximately 60 minutes every 2 weeks for 9 cycles. Lirilumab will be administered at 3 mg/kg IV over approximately 60 minutes once every 4 weeks. One cycle will be defined as 4 weeks.

Azacitidine+ lirilumab: Azacitidine 75 mg/m² IV daily x 7 days and lirilumab 3 mg/kg IV over approximately 60 minutes on day 7. A cycle will be considered 4 weeks.

Azacitidine+ lirilumab + Nivolumab: Azacitidine 75 mg/m² IV daily x 7 days followed on day 7 by nivolumab and lirilumab and nivolumab also on day 21. A cycle will be

considered 4 weeks. Doses of nivolumab and lirilumab are 3 mg/kg IV each over approximately 60 minutes.

Dose Adjustments

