11.0 Criteria for Response

For MDS, the International Working Group criteria will be use to assess response (11).

Remission is calculated from date of first response until relapse. Survival is calculated from start of therapy until death from any cause.

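### Duration of response is summarised by mean, SD, median and range with no censoring rule, so it will read too short if responses are ongoing at analysis

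*Combined protocol and SAP*

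**What the plan says.** Section 11.0 defines the quantity: "Remission is calculated from date of first response until relapse". It does not say what happens to a responder who has not relapsed.

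The Statistical Analysis Plan part of Section 15.0 handles duration of response in a parenthesis within the sentence on demographic and clinical characteristics: "including duration of response) and safety data of the patients will be summarized using descriptive statistics such as mean, standard deviation, median and range". Later in the same paragraph, Kaplan-Meier is assigned to other endpoints: "time-to-event endpoints (PFS and OS) including overall survival and event free survival will be estimated using the method of Kaplan and Meier". Duration of response is not named there.

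On timing, Section 15.0 states: "Overall response will be assessed after 6 cycles of treatment; cycle length is 28 days". Section 7.0 sets no fixed end of treatment; it continues until progression, intercurrent illness, patient request, a change in condition or toxicity. No section gives a follow-up length or a data cutoff.

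**The concern.** Time from first response to relapse is a time-to-event quantity. When some responders have not relapsed, their recorded time is only a lower bound. An analyst who follows the text has two ways to produce a mean and median: enter time to last follow-up as if it were complete, or keep only the patients who relapsed. The first pulls the mean down and can pull the median down. The second selects the short durations.

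Ongoing responses at analysis are plausible. Six cycles of 28 days is 168 days, about 5.5 months. If the analysis is run when the last patient reaches that assessment, that patient has at most 5.5 months of follow-up after response.

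Readers will look at this figure. Section 2.0 gives as part of the rationale that, with hypomethylating agents, "duration of response is usually limited and the prognosis of patients with HMA failure is extremely poor", and says the pilot data should guide larger trials. A figure that is too short would understate how durable responses are. What is at stake is the reporting of activity, not the design.

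**Working it through.** The plan states no figure for duration of response, so there is none to reproduce. The check asks how far plain summaries fall from the truth under stated assumptions.

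**Inputs from the documents.** Section 15.0: "Each cohort will be composed of N=20 patients". The standard and target ORR are 50% and 70%, which gives 10 to 14 responders per cohort; 12 (60%) is used below.

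**Assumptions (not in the documents).** Durations T are exponential with true median m of 6, 12 or 18 months. Follow-up after response, C, is independent of T and uniform on (a, b) months.

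**Formulas.** With λ = ln 2 / m:
- True mean = 1/λ. For m = 12 this is 12 / 0.693 = 17.3 months.
- Share censored = [exp(−λa) − exp(−λb)] / [λ(b − a)].
- Plain mean, with ongoing responses entered as complete = (1 − share censored) / λ.
- The large-sample plain median is the t that solves exp(−λt) × P(C > t) = 0.5. If every C exceeds m, the solution is m itself and there is no bias.

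**Example, m = 12, follow-up 0 to 24.** λ = 0.0578. Share censored = (1 − 0.25) / (0.0578 × 24) = 0.54. Plain mean = 17.3 × 0.46, about 7.9.

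The medians and the Kaplan-Meier column come from simulation (12 responders, 20,000 replicates per row). Medians are averages over replicates, in months.

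| True median (mean) | Follow-up | Censored | Plain mean | Plain median | Relapsed-only median | Kaplan-Meier median not reached |
|---|---|---|---|---|---|---|
| 6 (8.7) | 0–24 | 34% | 5.7 | 4.5 | 4.2 | – |
| 6 | 6–24 | 21% | 6.8 | 6.0 | 4.6 | – |
| 6 | 12–36 | 8% | 7.9 | 6.3 | 5.6 | – |
| 6 | 24–60 | 1% | 8.5 | 6.4 | 6.2 | – |
| 12 (17.3) | 0–24 | 54% | 7.9 | 6.8 | 5.5 | 20% |
| 12 | 6–24 | 44% | 9.7 | 9.1 | 6.0 | 14% |
| 12 | 12–36 | 27% | 12.6 | 11.7 | 8.2 | 1% |
| 12 | 24–60 | 11% | 15.5 | 12.7 | 10.8 | 0% |
| 18 (26.0) | 0–24 | 65% | 9.0 | 8.0 | 6.3 | 44% |
| 18 | 6–24 | 57% | 11.1 | 10.7 | 6.7 | 38% |
| 18 | 12–36 | 41% | 15.3 | 14.9 | 9.4 | 12% |
| 18 | 24–60 | 21% | 20.4 | 18.5 | 13.5 | 0.5% |

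(– : not tabulated.) The fair yardstick for the median columns is what 12 fully observed durations would give. That averages 12.7 for m = 12 and, by scaling, about 6.4 for m = 6 and 19 for m = 18. Plain medians with 10 or 14 responders lie within 0.2 months of those for 12.

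For m = 12 and 18 with follow-up 0 to 24, the middle Kaplan-Meier estimate over all runs, counting not reached as large, is 12.1 and 19.1. Averaged only over runs that reached it, it is 11.0 and 13.4.

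**Sequential cohorts.** Section 7.0 says "Accrual to cohort will be sequential in each patient group". Suppose both cohorts of a risk group are summarised at one cutoff, each accrues over 12 months, response comes 3 months after entry, and the true median is 12 in both. At month 30 the first cohort has 15 to 27 months of follow-up after response and the second 3 to 15. The plain medians are 12.0 and 6.5, and the plain means 12.1 and 6.8. At month 36 the medians are 12.6 and 10.0; at month 48 they are 12.7 and 12.6.

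**The case against.** The best case for the plan is that it under-specifies and does not choose a wrong method. Both lists are open-ended, so a Kaplan-Meier median is not forbidden, and nothing says ongoing responses count as complete or that only relapsed patients are summarised. That is a fair reading of the words. But the paragraph names Kaplan-Meier for other endpoints and puts duration of response elsewhere, and an analyst who did use Kaplan-Meier would still have no censoring date.

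Several other points stand and limit the weight:
- Duration of response is not named in the Section 1.0 objectives and drives no decision rule or planned comparison.
- The documents state no censoring rule for PFS, OS or event free survival either. Only the placement of duration of response is particular to it.
- All magnitudes rest on assumed inputs. The plain median shows almost no bias at a true median of 6 beyond the shortest follow-up, or at 12 once follow-up is at least 12 months.
- With few responders Kaplan-Meier does not always improve the median. With 14 responders, true median 12 and follow-up 12 to 36, the middle Kaplan-Meier estimate was 10.9 against a plain median of 11.8.
- The relapsed-only median of 6.2 (true median 6, longest follow-up) is above 6; it is short only against the 6.4 expected with complete data.
- The cohort contrast depends on a common cutoff that the documents do not state.
- Section 10.0 leaves marrow sampling after response to the treating physician. Relapse and censoring dates will be coarse and their timing may be informative, which Kaplan-Meier does not cure. Nor does it make plain summaries of censored durations sound.

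**Conclusion.** The concern holds. Applied as written with responses still ongoing, the Section 15.0 summary gives a mean that is too short, and a relapsed-only summary is shorter than complete follow-up would give. The plain median is too short only when a material share of follow-up falls below the true median.

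With a true median of 12 months and 12 responders, the plain median ranges from 6.8 (follow-up 0 to 24) to 12.7 (24 to 60, no bias), and the plain mean from 7.9 to 15.5 against 17.3. This rests on exponential durations, independent uniform censoring and exactly dated relapses, none of which the documents supply. If every responder has relapsed by the analysis, the problem does not arise. The effect is confined to a supportive summary of activity.

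**What to change.** In Section 15.0, take duration of response out of the descriptive-statistics sentence and add after the Kaplan-Meier sentence: *Duration of response among responders will be estimated by Kaplan-Meier, with responders in ongoing response censored at last disease assessment; the median with 95% CI (or not reached) and the number censored will be reported.*

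Separately, Section 11.0 could state whether death without relapse is an event or is censored and, unless the response criteria it adopts already settle this, what ends a response that was hematological improvement only. These definitions are the sponsor's choice and the main point does not depend on them.

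The change is to wording in Section 15.0, and in Section 11.0 if the definitions are added; both are protocol text. It needs no new design, sample size or software, though the censoring date is only as good as the post-response assessments actually made. The statistical cost is that a median may have to be reported as not reached. With 10 to 14 responders and follow-up of 0 to 24 months, this happens in about 18–22% of runs at a true median of 12 and 43–45% at 18.
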